#### Full Analysis Set

This table will be similar to 14.2.1.1.1.

Footnotes will be:

Note: CGI-S = Clinical Global Impression - Severity of Illness Scale, LSM = Least Squares Mean, SE = Standard Error, CI = Confidence Interval, N = number of subjects in the full analysis set by treatment group.

Note: Baseline is defined as the last non-missing measurement taken prior to first dose of double-blind study medication.

Note: CGI-S score is determined by answering the question "Considering your total clinical experience with this particular population, how mentally ill is the subject at this time?" on a scale of 0-7, with 0 indicating not assessed and 7 indicating the most extremely ill subjects.

Note: The mixed linear repeated measures model includes treatment, country, visit, treatment by visit interaction, and baseline value as covariates, and subject as random effect. The correlation of repeated measures within a subject is estimated with an unstructured covariance matrix. The Kenward-Rogers method is used to estimate the denominator degrees of freedom.

Note: Adjusted p-values are calculated according to the Hochberg procedure. Adjustment for multiple comparisons uses a parallel gatekeeping procedure. Adjusted p-values are presented for the secondary endpoint CGI-S Score change from baseline only if at least one of the primary hypotheses for the primary endpoint PANSS total score change from baseline are rejected.

### Table 14.2.2.2 Treatment Comparison of Change from Baseline in CGI-S Score at Week 6 – Pattern-Mixture Model Full Analysis Set

Tun Analysis Set

This table will be similar to 14.2.1.1.2.

Footnotes will be:

Note: CGI-S = Clinical Global Impression - Severity of Illness Scale, LSM = Least Squares Mean, SE = Standard Error, CI = Confidence Interval, N = number of subjects in the full analysis set by treatment group.

Note: CGI-S score is determined by answering the question "Considering your total clinical experience with this particular population, how mentally ill is the subject at this time?" on a scale of 0-7, with 0 indicating not assessed and 7 indicating the most extremely ill subjects.

Note: Baseline is defined as the last non-missing measurement taken prior to first dose of double-blind study medication. Note: A pattern-mixture model approach using a placebo-based multiple imputation has been used for this analysis.

Note: Imputed datasets are analyzed with the mixed linear repeated measures model including treatment, country, visit, treatment by visit interaction, and baseline value as covariates, and subject as random effect. The correlation of repeated measures within a subject is estimated with an unstructured covariance matrix. The Kenward-Rogers method is used to estimate the denominator degrees of freedom.

### Table 14.2.2.3 Treatment Comparison of Change from Baseline in CGI-S Score at Week 6 – Pattern-Mixture Model for Dropout Pattern 2

### Full Analysis Set

This table will be similar to 14.2.1.1.2.

Footnotes will be:

Note: CGI-S = Clinical Global Impression - Severity of Illness Scale, LSM = Least Squares Mean, SE = Standard Error, CI = Confidence Interval, N = number of subjects in the full analysis set by treatment group.

Author:	[name]	Version Number:	Draft 2
	Version Date:	09Jan2017	
			Page 44 of 144

Note: CGI-S score is determined by answering the question "Considering your total clinical experience with this particular population, how mentally ill is the subject at this time?" on a scale of 0-7, with 0 indicating not assessed and 7 indicating the most extremely ill subjects.

Note: Baseline is defined as the last non-missing measurement taken prior to first dose of double-blind study medication. Note: A pattern-mixture model approach using a placebo-based multiple imputation for discontinuation due to lack of efficacy, adverse event, or death has been used for this analysis.

Note: Imputed datasets are analyzed with the mixed linear repeated measures model including treatment, country, visit, treatment by visit interaction, and baseline value as covariates, and subject as random effect. The correlation of repeated measures within a subject is estimated with an unstructured covariance matrix. The Kenward-Rogers method is used to estimate the denominator degrees of freedom.

### Table 14.2.2.4 Treatment Comparison of Change from Baseline in CGI-S Score at Week 6 – Pattern-Mixture Model for Dropout Pattern 3

### Full Analysis Set

This table will be similar to 14.2.1.1.2.

Footnotes will be:

Note: CGI-S = Clinical Global Impression - Severity of Illness Scale, LSM = Least Squares Mean, SE = Standard Error, CI = Confidence Interval, N = number of subjects in the full analysis set by treatment group.

Note: CGI-S score is determined by answering the question "Considering your total clinical experience with this particular population, how mentally ill is the subject at this time?" on a scale of 0-7, with 0 indicating not assessed and 7 indicating the most extremely ill subjects.

Note: Baseline is defined as the last non-missing measurement taken prior to first dose of double-blind study medication. Note: A pattern-mixture model approach using a placebo-based multiple imputation for discontinuation due to lack of efficacy has been used for this analysis.

Note: Imputed datasets are analyzed with the mixed linear repeated measures model including treatment, country, visit, treatment by visit interaction, and baseline value as covariates, and subject as random effect. The correlation of repeated measures within a subject is estimated with an unstructured covariance matrix. The Kenward-Rogers method is used to estimate the denominator degrees of freedom.

## Table 14.2.2.5 Time-to-Failure Analysis Based on Change from Baseline in CGI-S Score and Dropout Pattern 1 Full Analysis Set

This table will be similar to 14.2.1.2.3. Footnotes will be: Note: CGI-S = Clinical Global Impression - Severity of Illness Scale, N = number of subjects in the full analysis set by treatment group.

Note: CGI-S score is determined by answering the question "Considering your total clinical experience with this particular population, how mentally ill is the subject at this time?" on a scale of 0-7, with 0 indicating not assessed and 7 indicating the most extremely ill subjects.

Note: a subject is considered to have failed if there is never an improvement in CGI-S score >=20% during the study or if there is an improvement >=20% during the study but a subsequent change from baseline <20%, or if the subject discontinues for any reason. Note: Time to Failure is calculated based on Kaplan-Meier methodology.

Note: Percentages are calculated as (n/N) \*100.

Author:	[name]	Version Number:	Draft 2
	Version Date:	09Jan2017	
			Page 45 of 144

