PMM analysis may also be performed according to patterns 2 and 3. For these analyses, only the discontinuation reasons considered as informative will be imputed using the placebo-based imputation model; discontinuations for non-informative reasons will be multiply imputed using the MAR assumption within each treatment arm. PMM analyses for pattern 2 and/or pattern 3 may only be performed if dropout is considered high.

**Scenario #2**: A continuous responder analysis based on improvement from baseline in PANSS total score will also be performed as described in Section 15.3.1.9.

Scenario #3: Time-to-failure analysis will combine two types of missing data (missing at random and missing not at random). Time-to-failure analysis will be performed treating informative missing data as failures following pattern 1, 2, and 3, and using censoring rules for non-informative cases. Time to failure will be calculated from the first PANSS score after baseline that is <20% improvement from baseline if there is never an improvement in PANSS score >=20% during the study or from the first PANSS score that is <20% improvement from baseline after a timepoint with >=20% improvement.

Document:	\\quintiles.net\Enterprise\Apps\sasdata\SASb\SAS\Noven\HP-			
	3070\XWA17541\Biostatistics\Documentation\SAP\Final 6\Noven HP-3070-GL-04 SAP text Final			
	6_18Jan2018.docx			
Author:	[name]	Version Number:	Final 6	
		Version Date:	18Jan2018	
Template No:	CS TP BS016 – Revision 3	Reference: C	CS WI BS005	

Effective Date: 01May2012

Copyright © 2012 Quintiles Transnational Corp. All rights reserved.

Noven Pharmaceuticals, Inc. STATISTICAL ANALYSIS PLAN: PROTOCOL HP-3070-GL-04 Page 29 of 50

**Scenario #4**: Analysis of Covariance (ANCOVA) on rank-transformed data at Week 6, adjusted for baseline and country, will be also performed as sensitivity analysis.

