# **15.2. Key Secondary Efficacy**

#### 15.2.1. Key Secondary Efficacy Variables & Derivations

#### 15.2.1.1. Change in CGI-S Score Between Baseline and Week 6

The severity of illness for each subject will be rated using the CGI-S. To perform this assessment, the rater or Investigator will answer the following question: "Considering your total clinical experience with this particular population, how mentally ill is the subject at this time?" Response choices include: 0 = not assessed; 1 = normal, not at all ill, 2 = borderline mentally ill; 3 = mildly ill; 4 = moderately ill; 5 = markedly ill; 6 = severely ill; and 7 = among the most extremely ill subjects.

Numerical values 1 through 7 corresponding to each response category (except "not assessed" category) will be used in analysis. The category of "not assessed" will be treated as a missing numerical value for analysis.

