#### **15.2.3.** ANALYSIS OF KEY SECONDARY EFFICACY VARIABLES

Analysis of the key secondary efficacy endpoint will be performed for the Full Analysis Set with multiplicity adjustment as described in Section 7.4.

Change from Baseline in CGI-S score at Week 6 will be analyzed in the same way as described in Section 15.1.3 for the primary endpoint, with the only difference that the MMRMs will use Baseline value of CGI-S as covariate instead of Baseline PANSS total score.

Document:	\\quintiles.net\Enterprise\Apps\sasdata\SASb\SAS\Noven\HP-			
	3070\XWA17541\Biostatistics\Documentation\SAP\Final 6\Noven HP-3070-GL-04 SAP text Final			
	6_18Jan2018.docx			
Author:	[name]	Version Number:	Final 6	
		Version Date:	18Jan2018	
Template No: CS_TP_BS016 – Revision 3		Reference: CS_WI_BS005		

Copyright © 2012 Quintiles Transnational Corp. All rights reserved.

Noven Pharmaceuticals, Inc. STATISTICAL ANALYSIS PLAN: PROTOCOL HP-3070-GL-04 Page 30 of 50

Sensitivity analysis of the key secondary endpoint will be performed in the same way as described in Section 15.1.4 for the primary endpoint.

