	6_18Jan2018.docx		
Author:	[name]	Version Number:	Final 6
		Version Date:	18Jan2018
Template No:	CS_TP_BS016 - Revision 3	Reference: (	S WL BS005

Effective Date: 01May2012

Copyright © 2012 Quintiles Transnational Corp. All rights reserved.

Noven Pharmaceuticals, Inc. STATISTICAL ANALYSIS PLAN: PROTOCOL HP-3070-GL-04 Page 31 of 50

passive/apathetic social withdrawal, difficulty in abstract thinking, lack of spontaneity and flow of conversation, stereotyped thinking.

If one or more items in the subscale are missing at a given assessment, the subscale score will be set to missing.

#### 15.3.1.7. Change from Baseline in PANSS General Psychopathology Subscale at Weeks 1 through 6

PANSS General Psychopathology Subscale is a sum of 16 items: somatic concern, anxiety, guilt feelings, tension, mannerisms and posturing, depression, motor retardation, uncooperativeness, unusual thought content, disorientation, poor attention, lack of judgment and insight, disturbance of volition, poor impulse control, preoccupation, and active social avoidance.

If one or more items in the subscale are missing at a given assessment, the subscale score will be set to missing.

# 15.3.1.8. PANSS Responder Based on ≥30% Improvement from Baseline in PANSS total score at Weeks 1 through 6

At each time point, subjects having a 30% or greater improvement from baseline in PANSS total score will be defined as "responders".

The PANSS total score percentage change will be defined as (Value at Week X – Baseline value) X 100 / (Baseline value).

The responder indicator will be set to 1 if the percentage change is less than or equal to -30% and set to 0 if the percentage change is greater than -30% or missing.

# 15.3.1.9. PANSS Responder Based on >=X% Improvement from Baseline in PANSS total score at Week 6

At Week 6, responder status will be derived in a similar way as described in section 15.3.1. 8 at different levels of required percent improvement from baseline where X=5% to 100% with 5% increments.

A continuous responder analysis will be performed based on these derivations as described in Section 15.3.3.3.

#### 15.3.1.10. Change from Baseline in CDSS Score at Weeks 1 through 6

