### Table 14.2.2.6 Time-to-Failure Analysis Based on Change from Baseline in CGI-S Score and Dropout Pattern 2 Full Analysis Set

This table will be similar to 14.2.1.2.3. Footnotes will be:

Note: CGI-S = Clinical Global Impression - Severity of Illness Scale, N = number of subjects in the full analysis set by treatment group.

Note: CGI-S score is determined by answering the question "Considering your total clinical experience with this particular population, how mentally ill is the subject at this time?" on a scale of 0-7, with 0 indicating not assessed and 7 indicating the most extremely ill subjects.

Note: a subject is considered to have failed if there is never an improvement in CGI-S score >=20% during the study or if there is an improvement >=20% during the study but a subsequent change from baseline <20%, or if the subject discontinues due to lack of efficacy, adverse event, or death. Discontinuations for other reasons are censored at discontinuation date.

Note: Time to Failure is calculated based on Kaplan-Meier methodology.

Note: Percentages are calculated as (n/N) \*100.

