### Table 14.2.2.7 Time-to-Failure Analysis Based on Change from Baseline in CGI-S Score and Dropout Pattern 3 Full Analysis Set

This table will be similar to 14.2.1.2.3. Footnotes will be:

Note: CGI-S = Clinical Global Impression - Severity of Illness Scale, N = number of subjects in the full analysis set by treatment group.

Note: CGI-S score is determined by answering the question "Considering your total clinical experience with this particular population, how mentally ill is the subject at this time?" on a scale of 0-7, with 0 indicating not assessed and 7 indicating the most extremely ill subjects.

Note: a subject is considered to have failed if there is never an improvement in CGI-S score >=30% during the study or if there is an improvement >=30% during the study but a subsequent change from baseline <30%, or if the subject discontinues due to lack of efficacy. Discontinuations for other reasons are censored at discontinuation date.

Note: Time to Failure is calculated based on Kaplan-Meier methodology.

Note: Percentages are calculated as (n/N)\*100.

### Table 14.2.2.8 ANCOVA on Rank-Transformed CGI-S Score Data at Week 6

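### The 20% CGI-S failure cut in Tables 14.2.2.5 and 14.2.2.6 asks for one point of improvement at baseline 4 or 5 but two points at baseline 6 or 7

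*SAP*

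**What the plan says.** Scenario #3 in SAP Section 15.1.4 defines time to failure for the PANSS total score. A subject who never reaches the cut ("if there is never an improvement in PANSS score >=20% during the study") has the failure timed at the first post-baseline score below 20%. A subject who reaches 20% and later drops below it fails at that later score.

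Section 15.2.3 extends this to the key secondary endpoint: "Sensitivity analysis of the key secondary endpoint will be performed in the same way as described in Section" 15.1.4. It gives no CGI-S version of the threshold.

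The table shells supply one:

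- Table 14.2.2.5 (dropout pattern 1): "a subject is considered to have failed if there is never an improvement in CGI-S score >=20% during the study", or if there is "improvement >=20% during the study but a subsequent change from baseline <20%, or if the subject discontinues for any reason".
- Table 14.2.2.6 (dropout pattern 2): failure "if there is never an improvement in CGI-S score >=20% during the study", with the same loss-of-improvement clause. Only discontinuations for lack of efficacy, adverse event or death count as failures; the others are censored.
- Table 14.2.2.7 (dropout pattern 3) departs from this: "a subject is considered to have failed if there is never an improvement in CGI-S score >=30% during the study".

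Section 15.2.1.1 sets the scale for analysis: "Numerical values 1 through 7 corresponding to each response category", with not-assessed treated as missing. The SAP's only percent-change formula is in Section 15.3.1.8, for PANSS, and divides by the raw baseline score: "Value at Week X – Baseline value) X 100 / (Baseline value".

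**The concern.** A 20% threshold suits a PANSS total score that runs from 30 to 210, because the scale has enough steps for the cut to fall close to 20% at any baseline. CGI-S has seven categories. On so coarse a scale, a percent cut becomes a whole number of categories, and that number jumps from one to two between baseline 5 and baseline 6. Nothing in the SAP suggests that this jump was intended.

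Section 7.3 presents the sensitivity analyses as a check that the primary and key secondary results are robust to missing data. For that purpose, the failure rule should count improvement much as the endpoint under test does. The key secondary endpoint is change in points, with baseline CGI-S as a covariate. The time-to-failure shell reports Kaplan-Meier quantities and a log-rank p-value, and states no baseline adjustment. If this table disagrees with the MMRM, the reader cannot tell whether dropout or the step in the failure rule is the cause.

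**Working it through.** **Inputs.** CGI-S takes whole numbers 1 to 7 (Section 15.2.1.1). The failure cut is 20% for patterns 1 and 2 (Tables 14.2.2.5 and 14.2.2.6) and 30% for pattern 3 (Table 14.2.2.7). Percent change is on the raw score (Section 15.3.1.8, borrowed from PANSS because no CGI-S formula is given). The SAP states no figure of its own on this point, so there is none to reproduce.

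**Formula.** Percent improvement = points gained / baseline score x 100. The cut is met when this is 20 or more.

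| Baseline CGI-S | One-point gain | Meets 20%? | Smallest gain that meets 20% |
|---|---|---|---|
| 2 | 1/2 = 50.0% | yes | 1 |
| 3 | 1/3 = 33.3% | yes | 1 |
| 4 | 1/4 = 25.0% | yes | 1 |
| 5 | 1/5 = 20.0% | yes, exactly | 1 |
| 6 | 1/6 = 16.7% | no | 2 (33.3%) |
| 7 | 1/7 = 14.3% | no | 2 (28.6%) |

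**Two subjects compared.** Both stay in the study, and both hold a one-point gain from the first post-baseline visit. The one going from 5 to 4 reaches 20% and does not fail. The one going from 6 to 5 never reaches 20%. Under the timing rule of Section 15.1.4, that subject fails at the first post-baseline visit, the earliest possible time. The key secondary endpoint records -1 for each.

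**Loss-of-improvement clause.** The same step appears here. A subject going 5, 3, 4 moves from 40% to 20% improvement and does not fail. A subject going 6, 4, 5 moves from 33.3% to 16.7% and fails, although both finish one point better than baseline.

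**Contrast with PANSS.** The same cut rises gradually there: 0.20 x 80 = 16 points, 0.20 x 90 = 18, 0.20 x 100 = 20, 0.20 x 120 = 24. No adjacent baselines differ by a doubling.

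**Dependence on the formula.** If the scale minimum of 1 were subtracted from the denominator, one point would be 1/3 = 33.3%, 1/4 = 25.0%, 1/5 = 20.0% and 1/6 = 16.7% at baselines 4, 5, 6 and 7. Only baseline 7 would then miss the cut. The SAP does not provide for this.

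**Pattern 3.** Against 30%, a one-point gain fails at every baseline from 4 to 7. The points needed are 2 at baselines 4 to 6 and 3 at baseline 7, since 2/7 = 28.6%. The split between 4-5 and 6-7 therefore does not occur in Table 14.2.2.7.

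**The case against.** The strongest reply is that every percent rule asks for more points at a higher baseline, and that a percent or absolute cut in a supportive analysis is a matter of preference. That is true of percent rules in general. It does not explain a requirement that doubles between two adjacent categories; that comes from the resolution of the scale.

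The reply is right on several other points, and they limit what can be concluded:

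- A reader might infer that the rule biases the comparison of HP-3070 with placebo or inflates type I error. The documents do not support this. The cut is the same in every arm, subjects are randomised 1:1:1, and the multiplicity procedure in Section 7.4 covers only the primary and key secondary analyses.
- A reader might infer that the robustness of the CGI-S result rests on these tables. It does not. The placebo-based imputation analyses and the rank ANCOVA (Tables 14.2.2.2 to 14.2.2.4 and 14.2.2.8) work on point change and use no percent cut.
- A reader might want to say how many subjects are misclassified. The SAP gives neither the baseline CGI-S distribution nor the frequency of one-point gains. Some one-point improvers at baseline 6 or 7 would also fail under any rule, because they lose the gain or discontinue for a counted reason.
- A one-point gain at baseline 4 or 5 does not by itself avoid failure. It must be held, with no counted discontinuation.

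**Conclusion.** The point stands as a minor one, for Tables 14.2.2.5 and 14.2.2.6 only. Applied to CGI-S, the borrowed 20% cut requires one point at baselines 2 to 5 and two points at 6 and 7. It therefore gives opposite failure status to subjects whom the key secondary endpoint treats as equal. This weakens the interpretability and sensitivity of a supportive time-to-failure analysis and goes no further.

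The conclusion assumes raw-score percent change, which is the natural reading of the SAP but is not stated for CGI-S. Under a minimum-adjusted formula the step would move to between baselines 6 and 7 and would not disappear. The number of subjects affected is unknown and cannot be derived from the SAP.

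The 30% cut in Table 14.2.2.7 is a separate matter. It conflicts with Section 15.1.4, which gives a single 20% rule for all three dropout patterns.

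**What to change.** Add a CGI-S sentence to Section 15.2.3, and change the failure footnotes of Tables 14.2.2.5 and 14.2.2.6 to an absolute cut. Failure is then never achieving at least a one-point improvement from baseline, or losing that improvement after it was reached, or a discontinuation that is informative under the pattern in question. One point is what the present cut already requires at baselines 4 and 5, so the change takes effect only at 6 and 7. Separately, reconcile the threshold in Table 14.2.2.7 with Section 15.1.4.

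The cost is one sentence, two footnotes and one programming condition, with no new data. The downside is that the rule becomes less demanding for subjects at baseline 6 or 7. A two-point cut would be equally uniform, but it would raise the requirement at baselines 4 and 5.

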### Table 14.2.2.6 Time-to-Failure Analysis Based on Change from Baseline in CGI-S Score and Dropout Pattern 2 Full Analysis Set

This table will be similar to 14.2.1.2.3. Footnotes will be:

Note: CGI-S = Clinical Global Impression - Severity of Illness Scale, N = number of subjects in the full analysis set by treatment group.

Note: CGI-S score is determined by answering the question "Considering your total clinical experience with this particular population, how mentally ill is the subject at this time?" on a scale of 0-7, with 0 indicating not assessed and 7 indicating the most extremely ill subjects.

Note: a subject is considered to have failed if there is never an improvement in CGI-S score >=20% during the study or if there is an improvement >=20% during the study but a subsequent change from baseline <20%, or if the subject discontinues due to lack of efficacy, adverse event, or death. Discontinuations for other reasons are censored at discontinuation date.

Note: Time to Failure is calculated based on Kaplan-Meier methodology.

Note: Percentages are calculated as (n/N) \*100.

